### Methods and timing for assessing, recording, and analyzing variables

Table 4. Overview of outcome measures of assessment during the study

ALICE-Client			
	Outcome measure	Type of test	Name of test/questionnaire
Effectiveness	Speech understanding in difficult listening situations	Speech in noise test Questionnaires	Lafon disyllabiques
	Listening effort		SSQ12 (Gatehouse and Noble, 2004) COSI (Dillon et al., 1997)
	Emotional consequences /acceptance of HI		EAS (Alhanbali et al., 2017)
	Use of hearing aid and care delivery		CAS (Öberg et al., 2021)
			ALICE-Specific questionnaire (custom made)

#### Overview of the tests and questionnaires used:

(all materials are added to the folder CIP\_materials)

The “**listes disyllabiques de Lafon**” is validated speech material consisting of French disyllabic words that can be presented in quiet or in noise (Marie-Haps procedure). This speech material is included in the investigation because it is commonly used in the standard clinical practice in the Walloon region and Brussels. Administering this test is also a part of the RIZIV/INAMI application process to receive a reimbursement for hearing aids.

The **SSQ12** is a short version of the validated Speech, Spatial and Qualities of Hearing Scale, developed for use in clinical research and rehabilitation settings (Noble et al., 2013). The SSQ questionnaire has also been validated in French (Moulin et al., 2015). For the purpose of this research arm, we have constructed a French short version.

The **COSI** questionnaire (Client Oriented Scale of Improvement) was explained in detail in the context of ARM 1 (3.5.6.2) and ARM 2 (3.5.6.3) and will be administered in French in ARM 3. The administration of this questionnaire is also a part of the RIZIV/INAMI application process to receive a reimbursement for hearing aids.

The **CAS** (Communication and Acceptance Scale) and **EAS** (Effort Assessment Scale) have been explained in the context of ARM 1 (3.5.6.2) and/or ARM 2 (3.5.6.3) and have been translated from Dutch to French for the purpose of this arm of the clinical trial.

The **ALICE-questionnaire** was developed for the purpose of this study. The questions of this questionnaire were based on 3 different questionnaires. First, the SUS (system usability scale) to determine the usability of the ALICE app. Second, the SADL (Satisfaction with Amplification in Daily Living) which was designed to evaluate the satisfaction that people experience with their hearing aids. Third, the PREM (Patient Reported Experience Measures) as is used to evaluate audiological centres in the Netherlands. A total of 20 questions were selected to evaluate the participants’ experience with the usability of the ALICE app, their satisfaction with their hearing aids and their satisfaction with their audiologist/hearing centre.

Equipment to be used for assessing the clinical investigation variables and arrangements for monitoring maintenance and calibration.

*Equipment used/needed to perform test protocol*

- Speech in noise testing: part of the standard of care
  - o Audiometer (calibrated): available at the investigational sites
- Questionnaires: online/tablet
  - o Clients will be able to fill out the questionnaires on a tablet (provided by the KU Leuven researchers to the investigational sites) or on their own computer through a website
- The app will be used on the clients' personal smart device (device compatibility is described in the IB)
- Feedback: documented in word files

Clinical investigation sites: number, location and if appropriate differences in clinical investigation site characteristics.

A list of participating clinical investigation sites and their locations will be provided at a later stage.

**Subjects**

Subjects will be recruited by their HCP (see recruitment procedure) in accordance with the following criteria:

*Inclusion criteria*

- Clients who are using a hearing aid (N = 120), which is more than necessary according to the power analysis (3.5.7). Clients must have completed the hearing aid trial period and must have decided to purchase the hearing aid.
- Clients who experience listening and communication difficulties
- Clients with a hearing aid may not have any experience with auditory training yet.
- Able to operate the training programme as an app on a mobile device/tablet (e.g. clients have a mobile device or table; clients have sufficient eyesight to see the exercises; clients must be able operate the program).
- At least 18 years old.
- French-speaking as all instructions and counselling questions will be presented in French.
- Clients need to have an Android or iPhone smartphone and connection to internet.

*Exclusion criteria*

- Visually impaired
- Motorically impaired
- Cognitively impaired

**Criteria and procedures for subject withdrawal or lost to follow up**

*When and how to withdraw a subject from the clinical investigation or stop the use of the investigational device*

Clients participate in this study voluntarily and have the right to withdraw from the study at any time they want. If they choose to withdraw they will be asked to delete the ALICE app from their smartphone or tablet.

*Documentation of efforts to be made to trace subjects that are lost to follow up and possible reasons*

When clients withdraw from the study, they will be asked to provide a reason as this may be of interest to the study. However, they are not obligated to provide a reason for their withdrawal.

### *Whether and how subjects are to be replaced*

In case of withdrawal or loss to follow up, we will report this but the client will not be replaced since we have sufficient participants for the study.

## Procedures

### *Overview and estimated timing*

### *Enrolment of investigator sites*

- 8 hearing centres will be enrolled as an investigator site in this multicentric study. The sites will be assessed based on adequate resources, a qualified investigation team and access to an adequate number of subjects.
- For every investigator site, one local PI will be appointed. The local PI will be responsible to execute the investigation (following the study protocol) and to perform the local coordination for the study.
- In order to know if the local PI is eligible to coordinate the study, the following criteria apply
  - Experienced professionals (> 5 years of working experience) in the field of aural rehabilitation of adults with hearing impairment
  - French speaking
  - Willing to become familiar with research and good clinical practice
- Once the local PI has been assigned (and approved by FAGG and EC), the protocol will be discussed and the clinical trial agreement (see Annex 8) will be signed by the local PI.
- All local PI's will have to follow an initiation training, in which following details of the study are presented and/or discussed
  - Intended use of the app
  - Content of the investigator's brochure (IB)
  - Instructions for use of the ALICE app, with aids-on training with the app, including set-up and internal calibration
  - Recruitment protocol
  - Enrolment protocol with ICFs for the clients
  - Study programme with study protocol (= CIP), in which instructions are included to uniformly assess and document clinical findings (eCRF)
  - GCP (see GCP protocol)
  - Quality check of the in-house equipment that will be used
  - Coordination & assistance
  - Risk management

### *Recruitment of clients*

- The local study team (HCPs working in the hearing centre) of each investigator site will be responsible for the recruitment of patients. Before they start with recruiting they will be instructed with clear inclusion and exclusion criteria
- The number of clients that should be enrolled will be in the range of 15 to 20 persons for every investigator site

- The recruitment period is a fixed period over a time span of 12 weeks or when approximately 15 to 20 clients are recruited, after that period no clients can enter the study.

#### *Enrolment of clients*

- Clients who match the criteria, will receive a brief introduction about the study, which may or may not include the ALICE app. If they are interested to participate in the study, they will receive an information brochure about the study program, in which a more detailed description is provided (details about the course of the study, the 2 visits at 0 and 8 weeks, the duration of the study and their rights and responsibilities). They will also be informed that they will be assigned randomly to one of the three groups.
- If clients agree to participate in the study they will sign an informed consent form.
- A complete list of clients who wish to participate for each investigational site is sent to the KU Leuven researchers at the end of the recruitment period.
- After being stratified by age, clients will be randomly assigned to one of the two groups by a KU Leuven researcher using an automatic seed generator:
  - 1 group will receive the standard of care
  - 1 group will receive the standard of care with additional support of the ALICE app (French version)

	Responsible	Accountable
Clients match the criteria	Local PI	KUL PI
Clients get a brief introduction about the app and the goals of the study; when interested they receive a detailed information brochure	Local PI	
Clients sign an Informed Consent Form	Local PI	KUL PI
Clients are enrolled in the study	Local PI	KUL PI
Allocation of groups and randomization	KUL PI	KUL PI

#### *The study program and test protocol*

- Onboarding procedure: once the clients are enrolled they will receive a standard onboarding procedure, which will be led by the local PI. Within this procedure following points/formalities will be discussed with their client:
  - The study program/course of the study
  - Appointment schedule to perform the tests
  - Procedure to follow in case of change
  - Contact information in case of questions
  - Risk & Safety management (see safety section), with special attention to following procedures:
    - Procedure to control the loudness of the stimuli provided by the app
    - Procedure to follow to ensure safe data management (compliant with GDPR)
    - Procedure to follow in case of adverse events and/or device malfunction
  - Rights and responsibilities
- Installation of the app
  - Intended use of the app
  - Compatibility of the app with personal (streaming) devices,
  - Instructions to use the app

- First installation and set-up of account
- Test protocol (see below and Fig. 6)

*Description of all the clinical-investigation-related procedures that subjects undergo during the clinical investigation including any deviation from normal clinical practice*

Below (Figure 6), the timeline of the test protocol is presented: After allocation to a treatment group a client will be assessed with a speech in noise test and questionnaires, followed by 8 weeks use of the ALICE app. The same outcome measures will be assessed at the final appointment to evaluate the benefit of the intervention.

*Figure 6. Timeline of the test protocol.*

## Monitoring plan

*General outline of the monitoring plan to be followed, including access to source data and the extent of source data verification planned*

In accordance with ICH-GCP E6(R2) the Sponsor is responsible for monitoring the Trial to ensure compliance with GCP and current legislation, and to verify, among other requirements, that proper written informed consent has been obtained and documented, that the Trial procedures have been followed as shown in the approved protocol, and that relevant Trial data have been collected and reported in a manner that assures data integrity. To this end Source Data will be compared with the data recorded in the (e)CRF. A risk-based approach will be applied to determine the extent of monitoring activities and monitoring of the Trial will be performed by qualified individuals (independent from the site Trial staff), as applicable.

- **Coordination & monitoring plan**

- Project management and on-site monitoring visits

The Coordinating Investigator ([name], KUL) will supervise: the recruitment and the enrolment of the study participants (including the verification of the ICF procedure), the implementation of the study protocol at the investigational sites, the quality of the data collection, the achievement of the study goals, and the use of the ALICE app according to the CIP.

The test protocol will be performed by the local PI. The local PI can rely on support and assistance of the Coordinating Investigator at any given time. The Research Manager will schedule regular monitoring visits with the local PI. All monitoring activities will be documented in a written report according to ISO14155.

- Project support

- When clients need additional support, their first contact point will be their HCP of the local study team.
  - When the support needed is related to their hearing or hearing aids, the local study team will help them out through their standard of practice (standard care path).
  - When the support needed is related to the use of the app, the local study team will contact the Coordinating Investigator. The Coordinating Investigator will provide the local study team with additional support. If needed, technical support will be provided by our in-house developers.
- Safety evaluation & reporting
  - Adverse events, device deficiencies, and withdrawals will be reported and documented (see section 'Subjects' + withdrawal procedure section 3.5.6.4).
- Data collection
  - To ensure/guarantee quality of the data collection, the Coordinating Investigator will perform a quality check of the data (samples) on regular basis.
  - Safety = See data management plan

### 3.5.7. Statistical design and analysis

#### 3.5.7.1. Sample size

HCPs from the hearing centres participating in the first, second and third arm of the study will include a total of 390 hearing aid users (150 in the first arm, 120 in the second arm and 120 in the third arm). HCPs from UZ Leuven will include 30 CI users for the first arm only. Clients will be equally divided among participating investigation sites. After being stratified by age, they will be randomly assigned to two groups of approximately 195 hearing aid users (75 in the first arm, 60 in the second arm and 60 in the third arm), and two groups of 15 CI users (first arm only). One group will receive the standard of care, the other group will receive the standard of care supplemented with the ALICE app (The Dutch version in both the first and second arm the French version in the third arm).

Scientific literature was consulted to estimate the group size needed for our RCT and a power analysis was conducted to confirm the effect size for this sample.

Power analysis conducted with the G\*Power software (Erdfelder et al., 2009) indicated that a total sample of at least 76 persons is needed to detect differences in speech understanding in noise outcomes between the two treatment groups with a low to medium effect size ( $d = 0.25$ ) to have statistical power of 95% using a repeated measures ANOVA ( $\alpha = 0.05$ ). We will be able to recruit more clients via the hearing centers (between 15 and 30 persons per hearing center). We estimate that, for all three arms of the study, 390 persons with a HA will take part in the trial and, for the first arm of the study only, about 30 persons with a CI. This larger number accounts for clients being lost to follow-up during the study.

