### *Inclusion criteria*

- Clients who are using a hearing aid (N = 150) or cochlear implant (N = 30). Which is more than necessary according to the power analysis (3.5.7).
  - o Clients with a hearing aid must have completed the hearing aid trial period and must have decided to purchase the hearing aid.
  - o Clients with a cochlear implant must have at least 6 months of experience with the cochlear implant.
- Clients who experience listening and communication difficulties
- Clients with a hearing aid may not have any experience with auditory training yet.
- Able to operate the training programme as an app on a mobile device/tablet (e.g. clients have a mobile device or table; clients have sufficient eyesight to see the exercises; clients must be able to operate the programme).
- At least 18 years old.
- Dutch-speaking as all training material and counselling questions will be presented in Dutch.
- Clients need to have an Android or iPhone smartphone and connection to internet

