### *Inclusion criteria*

- Clients who are starting their hearing aid trial as a first time hearing aid user (N= 120). Which is more than necessary according to the power analysis (3.5.7).
- Clients who experience listening and communication difficulties
- Able to operate the training programme as an app on a mobile device/tablet (e.g. clients have a mobile device or table; clients have sufficient eyesight to see the exercises; clients must be able operate the programme).
- At least 18 years old.
- Dutch-speaking as all training material and counselling questions will be presented in Dutch.
- Clients need to have an Android or iPhone smartphone and connection to internet

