#### 3.5.7.2. Statistical analysis

Statistical analyses will be performed using either the R programming language and statistical environment (R Core Team, 2017) or IBM SPSS 27. Potential missing data will be replaced using multiple imputation (in SPSS).

Data for hearing aid users and cochlear implant users will be analysed separately. Potential relations between outcomes will be determined in a within-subject design, i.e., baseline session outcomes will be compared to the final session outcomes, with a repeated measures ANOVA ( $\alpha = 0.05$ ). We will correct for multiple comparisons using Dunn post-hoc tests with Holm correction (Dunn, 1961).

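### The 76-person power statement does not hold for d = 0.25 as labelled (15–40% power, not 95%, at correlations 0.3–0.8), its G*Power inputs are not given, and the 30 separately analysed CI users fall below 76

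*Combined protocol and SAP*

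**What the plan says.** Section 3.5.7.1 is the only sample-size justification, and 3.5.5.2 refers the effect size there. It states that "a total sample of at least 76 persons is needed to detect differences in speech understanding in noise outcomes between the two treatment groups", for an effect written as d = 0.25 and described as low to medium, "to have statistical power of 95% using a repeated measures ANOVA" at alpha 0.05. It does not give the type of F test, the number of groups and measurements entered, the correlation between measurements, or an SD.

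Planned enrolment is 150, 120 and 120 hearing aid (HA) users in Arms 1, 2 and 3, plus "two groups of 15 CI users (first arm only").

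Each arm's inclusion criteria rely on the power analysis. Arm 1 (3.5.6.2) names HA users and "cochlear implant (N = 30). Which is more than necessary according to the power analysis (3.5.7"). Arm 2 (3.5.6.3) adds to its N = 120: "Which is more than necessary according to the power analysis (3.5.7"). Arm 3 (3.5.6.4) says "Clients who are using a hearing aid (N = 120), which is more than necessary according to the power analysis (3.5.7").

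On analysis, 3.5.7.2 says "Data for hearing aid users and cochlear implant users will be analysed separately", and that "baseline session outcomes will be compared to the final session outcomes, with a repeated measures ANOVA". It names no group-by-time term and does not say whether the arms are pooled.

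**The concern.** A sample of 76 is far too small for 95% power at d = 0.25 between two groups, unless the baseline–final correlation is extremely high. So either the effect is not a Cohen's d, or the stated power is wrong. The sufficiency notes in all three arms rest on this one statement.

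As written, a null result could be read as excluding a small benefit (d = 0.25) that the trial may have had little chance of detecting. For CI users the difficulty does not depend on how d is read: they are analysed separately, and 30 is less than the total the plan says it needs.

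**Working it through.** **Inputs from the plan (3.5.7.1, 3.5.7.2):** effect 0.25; alpha 0.05; power 95%; two treatment groups allocated equally; two measurements (baseline and final); total N = 76. **Not in the plan:** the correlation rho between the two measurements, taken here as 0.3 to 0.8.

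**1. Reproducing 76.** For a repeated measures ANOVA with Cohen's f, k groups and m = 2 measurements, the noncentrality is lambda = f² × N × m / (1 − rho). With f = 0.25, N = 76 and rho = 0.3, lambda = 0.0625 × 76 × 2 / 0.7 = 13.57. Three routes lead to 76:

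| Route | Power at N = 76 |
|---|---|
| (i) group-by-time interaction, k = 2, rho 0.3 | 95.3% |
| (ii) group-by-time interaction, k = 4, rho 0.5 | 95.9% |
| (iii) time effect, k = 2, rho 0.3 | 95.3% |

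The two-group interaction at rho 0.5 needs 54. The between-groups test needs 138 (rho 0.3) or 158 (rho 0.5). So 76 is reproducible, but only with 0.25 as f and with inputs the plan does not give.

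**2. What f = 0.25 means.** In the two-group interaction, f = delta/4, where delta is the between-group difference in change in SD units. Hence f = 0.25 is delta = 4 × 0.25 = 1.0 SD. In the time effect, f = change/2, so f = 0.25 is an average change over time of 0.5 SD in both groups together. A between-group difference in change of 0.5 SD at N = 76 and rho 0.3 has only 44% power.

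**3. Reading 0.25 as d, as labelled.** Substituting f = delta/4 gives lambda = delta² × N / (8(1 − rho)), with 1 and N − 2 degrees of freedom. At delta = 0.25 and N = 76, lambda = 0.0625 × 76 / (8 × 0.7) = 0.85 at rho 0.3, 1.19 at rho 0.5 and 2.97 at rho 0.8. Power is 14.9%, 18.9% and 39.8%. It is 92.5% at rho 0.95 and 96.7% at rho 0.96, crossing 95% at about 0.955. The N needed for 95% power is 1168, 834 and 336 at rho 0.3, 0.5 and 0.8.

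Other conventions at N = 76, rho 0.3 to 0.8: final value only 18.9%; ANCOVA 20.4–43.4%; one-sided change score 23.5–53.1%; d converted to f = d/2 = 0.125 and entered as the interaction f, 44–92.5%. None reaches 95%.

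**4. Planned sizes, same group-by-time test.**

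| Population | Power at d = 0.25, rho 0.3–0.8 | Rho for 95% power | Difference in change detectable with 80% power (SD), rho 0.3 / 0.5 / 0.8 |
|---|---|---|---|
| N = 120 (Arm 2 or Arm 3) | 21–57% | 0.93 | 0.61 / 0.52 / 0.33 |
| N = 150 (Arm 1 HA) | 25–67% | 0.91 | 0.54 / 0.46 / 0.29 |
| N = 270 (Arms 1 and 3 HA pooled) | 41–90% | 0.84 | 0.40 / 0.34 / 0.22 |
| N = 390 (all HA pooled) | 55–97% | 0.77 | 0.34 / 0.28 / 0.18 |
| N = 30 (CI) | 9–18% | 0.98 | 1.25 / 1.06 / 0.67 |

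**5. CI users.** The 95% confidence half-width for the difference in change is t(28) × √(2(1 − rho)) × √(4/30) = 0.89, 0.75 and 0.47 SD at rho 0.3, 0.5 and 0.8. Even for f = 0.25 (1.0 SD), a two-group comparison of 30 has 61% power at rho 0.3 and 75% at rho 0.5, the correlations that reproduce 76. It would have 93% at rho 0.7 and 99% at rho 0.8, but 76 would not be the answer at those values.

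**The case against.** The strongest reply is that 76 is not a miscalculation: f was probably entered and then labelled d. On that reading the HA arms are well sized for the effect entered. At f = 0.25, two groups and rho 0.3, N = 120 gives 99.6% power and N = 150 gives 99.9%, and an arm of 120 could lose 44 people and still hold 76. This stands as the likely origin of the number. It does not rescue the text, because the target would then be a 1.0 SD difference in change, which is not low to medium. If the time effect was used, the group comparison was not sized.

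It is also fair that 3.5.7.2 names no group-by-time term, so the power figures assume the test that a comparison between treatment groups requires. Section 3.5.7.1 states that comparison as the target, so the assumption is reasonable, but it is an assumption.

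For CI users, the Arm 1 note could mean the combined 180, and 3.5.6.1 treats experienced HA and CI users as one user group. If route (ii) was used with the four Arm 1 cells (HA or CI, with or without the app), 76 would cover both device types and the CI share would be 38. But CI users are analysed separately, and 30 is below 38 as well as below 76.

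Finally, Arm 1 recruitment was probably over when this version was written, and the plan nowhere says that a null result would exclude a small effect. Both points are true, and they are why the remedy is restatement and not added enrolment. The stated power still has to be correct.

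**Conclusion.** The concern holds. As labelled, 76 persons give 15–40% power for d = 0.25 at correlations of 0.3 to 0.8, against the stated 95%, and no reading of 0.25 as d that was tried reaches 95% in that range. The range rests on an assumed correlation and on scaling d by the single-occasion SD.

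Mislabelling of Cohen's f is the probable explanation, but the documents do not show which test was run, and the possible tests imply different target effects. The planned HA samples do not settle the matter for a small effect: power at d = 0.25 is 21–67% for single arms and 55–97% if all 390 are pooled. The plan does not mention pooling. Separate analysis is assumed here as likely, because the arms use different speech tests (LIST, BLU, Lafon).

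The claim of sufficiency for CI users is unsupported whatever the correlation, since 30 is below the plan's own 76. This must be corrected because it is the trial's only sample-size justification.

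**What to change.** - **3.5.7.1:** Check the G*Power output and restate the calculation with the effect metric, F-test type, number of groups, number of measurements and correlation. Express the effect as a between-group difference in change in SD units. If the input was f, remove d = 0.25 and the low to medium description. If the time effect was used, say so and give the power of the group-by-time test instead.
- **3.5.7.1 and 3.5.7.2:** State whether arms are pooled. For each population analysed separately, give the difference detectable under the planned repeated measures ANOVA at its planned size, over a stated range of correlations.
- **Inclusion criteria, Arms 1, 2 and 3:** Align the sufficiency notes with the restated calculation and remove the note for CI users. Label the CI comparison exploratory, reported as an estimate with a confidence interval.

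The cost is wording, with no change to enrolment or visits. The stated power becomes less favourable for small effects, and the CI comparison gives up any confirmatory claim.

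### The two-session repeated measures ANOVA leaves the group comparison unadjusted for baseline; modelling the final score on group and baseline would be more precise using data already collected

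*Combined protocol and SAP*

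**What the plan says.** Section 3.5.7.1 (Sample size) reports a G*Power calculation: "a total sample of at least 76 persons is needed" "to detect differences in speech understanding in noise outcomes between the two treatment groups", with an effect size of 0.25 (labelled d), 95% power and alpha 0.05. The method named is a repeated measures ANOVA.

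Section 3.5.7.2 (Statistical analysis) uses the same method: "Potential relations between outcomes will be determined in a within-subject design", in which "baseline session outcomes will be compared to the final session outcomes, with a repeated measures ANOVA". It names neither a group term nor a group-by-session term. On incomplete data it says: "Potential missing data will be replaced using multiple imputation (in SPSS"; it does not say how results are combined over the imputed data sets.

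No section adjusts the final score for baseline, and none gives a baseline-final correlation. In Arm 1 speech in noise is measured at the first and final appointments (section 3.5.6.2). Arm 3 has visits at 0 and 8 weeks, with the same measures repeated at the end (section 3.5.6.4). Planned group sizes for hearing aid users are 75, 60 and 60 in Arms 1, 2 and 3. For cochlear implant (CI) users they are 15, in Arm 1 only.

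**The concern.** Each arm is a randomised superiority comparison, so the estimate of interest is the difference between groups at the end of the intervention period. A two-session repeated measures ANOVA can give a group comparison in two ways.

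- **Group-by-session term.** This is the t-test on final minus baseline. It fixes the slope of final on baseline at 1 instead of estimating it.
- **Group main effect.** This averages the pre-treatment session, where no effect can exist, with the final session, and so halves the effect.

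Either way precision is lost although the baseline score is already in hand. At stake are the width of the confidence interval and the power within each arm. The validity of the test is not in question.

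**Working it through.** **Inputs.** From section 3.5.7.1: total 76, effect size 0.25, power 95%, alpha 0.05, and the group sizes above. Assumed, because the documents do not give them: rho from 0.3 to 0.9, equal SDs (set to 1) at both sessions, and the true difference delta in SD units of the final score.

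**Reproducing 76.** I used the noncentral F for a group-by-session term with k groups and m sessions: noncentrality = f² × N × m/(1 − rho), with (k−1)(m−1) and (N−k)(m−1) degrees of freedom.

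- f = 0.25, 2 × 2, rho 0.3: N = 76 (noncentrality 0.0625 × 76 × 2/0.7 = 13.57).
- f = 0.25, 4 groups × 2 sessions, rho 0.5: N = 76.
- f = 0.125 (that is, d/2), 2 × 2, rho 0.825: N = 76.
- f = 0.25, 2 × 2, rho 0.5: N = 54.

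So 76 can be reached, but only with inputs the plan does not state, and it does not reveal rho. In the 2 × 2 interaction f equals delta/4, so f = 0.25 means a 1.0 SD difference in change and f = 0.125 means 0.5 SD.

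**Identity.** In a 2 × 2 layout the group-by-session F equals the squared change-score t (0.7445 both ways in a numerical check).

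**Variances.** Per client, the change score has variance 2(1 − rho) and the baseline-adjusted final score 1 − rho². The ratio of adjusted to change is (1 + rho)/2. The sample that would give the same precision under the change score is 120 × 2/(1 + rho).

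| rho | variance ratio | SE ratio | 120 clients adjusted are worth |
|---|---|---|---|
| 0.3 | 0.65 | 0.81 | 185 |
| 0.5 | 0.75 | 0.87 | 160 |
| 0.7 | 0.85 | 0.92 | 141 |
| 0.9 | 0.95 | 0.97 | 126 |

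**Power, 60 per group** (Arm 2 or 3). Power = Phi(delta/√(v × 2/60) − 1.96), where v is the per-client variance. Example at rho 0.5, delta 0.5: the change score gives 0.5/√(1.00/30) = 2.74, power 0.78; adjusted gives 0.5/√(0.75/30) = 3.16, power 0.89.

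| delta (assumed) | rho | change score | adjusted |
|---|---|---|---|
| 0.5 SD | 0.3 | 0.64 | 0.82 |
| 0.5 SD | 0.5 | 0.78 | 0.89 |
| 0.5 SD | 0.7 | 0.94 | 0.97 |
| 0.25 SD | 0.5 | 0.28 | 0.35 |
| 0.25 SD | 0.825 | 0.64 | 0.68 |

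**Group main effect.** The effect is delta/2 and the variance (1 + rho)/2. At delta 0.5 and rho 0.5: 0.25/√(0.75/30) = 1.58, power about 0.35.

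**Simulation** at 0.5 SD, rho 0.5 and 60 per group gave power of 77% (change), 87% (adjusted) and 33% (group main effect). Type I error was about 5% for both the change and adjusted tests over the null settings tried (3.9% to 5.6%).

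**CI users, 15 per group.** Estimating the slope inflates the adjusted variance by about 1 + 1/(N − 4) = 1 + 1/26 = 1.038. At rho 0.9 the net ratio is 0.95 × 1.038 = 0.99; at rho 0.95 it is 0.975 × 1.038 = 1.01. The gain is gone somewhere above 0.9.

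**The case against.** **The tested term is inferred.** Section 3.5.7.2 read literally is a within-subject comparison with no group factor. That stands: the change-score reading comes from taking 3.5.7.1 and 3.5.7.2 together. It does not rescue the plan, since neither available group term is adjusted for baseline, and writing out the model removes the ambiguity.

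**The method is not wrong.** A randomised change-score comparison is unbiased and holds its type I error. This is accepted; the point concerns efficiency only.

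**The power gain may be small.** The 0.5 SD effect is not in the plan. Under the two 2 × 2 input sets that reproduce 76, 60 per group already gives about 0.996 with the change score (1.0 SD at rho 0.3; 0.5 SD at rho 0.825), so adjustment adds almost nothing to power. This is fair: the 18-point gain needs rho 0.3 together with 0.5 SD. The narrower interval remains in every case.

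**Imputation.** A reader might infer that multiple imputation and the planned ANOVA cannot be combined. The documents do not support that. The two-session group-by-session term is a single contrast, a difference in mean change with a standard error, and Rubin's rules pool it directly. What is missing is a statement of how results are pooled.

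**First-time users.** A reader might also expect weak baseline-final correlation, and so the largest loss, in Arm 2. No section gives a correlation for any group.

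**Baseline after allocation.** Clients are tested after they are allocated. If knowing the allocation shifted the baseline score alone, the change score would carry the whole shift and the adjusted score only about rho times it, so this does not count against adjustment.

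**Scope.** Sections 3.5.6.2 to 3.5.6.4 can be read as giving the questionnaires twice before training, and Arm 2 has three visits. The case is firmest for speech in noise.

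**Conclusion.** The point holds as an avoidable loss of precision. If the groups are compared through the group-by-session term, adjusting for baseline cuts the variance by 35%, 25%, 15% or 5% at rho 0.3, 0.5, 0.7 or 0.9; the group main effect would be weaker than the change score for any positive rho. The direction follows from the design for any rho below 1, assuming equal SDs and groups large enough that a degree of freedom does not matter. The size rests on a rho, and for power on an effect, that the documents do not state. The planned test is not invalid, and the conclusion does not depend on the imputation plan.

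**What to change.** In section 3.5.7.2, for speech in noise and any other outcome measured at both sessions, state that the group comparison is a linear model of the final score on randomised group, the client's pre-training baseline score and age (the stratification factor). Report the adjusted group difference with a 95% CI, with the estimate and standard error pooled over imputations by Rubin's rules. For questionnaires given twice before training, state which score is the baseline. The 76 in section 3.5.7.1 can stay, labelled as based on the unadjusted repeated measures ANOVA.

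The cost is a change of wording; no extra data are collected. The model spends one degree of freedom for baseline and one for age if age enters as a single term. That is negligible in the hearing aid groups. With 15 CI users per group the gain may vanish if rho is above about 0.9.
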